5.6 Key exclusion criteria

- 1. Individuals who plan to move out of the study microcluster within 6 months
- 2. Individuals who are unable to fully consent and participate based on CC team assessment
- 3. Individuals who are not the primary caregivers of children ages 3-17 years

6. Subject recruitment

Participant recruitment will commence in September 2022 and will run through March 2024. Recruitment in control and intervention microclusters will occur simultaneously. The data analyst who performed the randomization will randomize microcluster order (stratified by intervention and control status and city section) to determine the order in which recruitment occurs.

Several Community Coordinator (CC) teams will be recruiting participants. A given team of two will remain in a microcluster until a total of 12 participants are fully enrolled in that microcluster. They will then move to the next microcluster on the randomly generated list. Multiple microclusters will be undergoing enrollment simultaneously. The CC team will be blinded to what arm of the trial the microcluster is in until all participants are enrolled. Participants will also be blinded until after everyone in that cluster is enrolled.

When starting recruitment in a new microcluster, the CC team will first place door knockers on all homes within the microcluster boundaries to alert neighbors to the presence of the study team in the neighborhood. They will then begin door-to-door recruitment at a pre-determined house that is closest to the geographic center of the study microcluster. They will follow a pre-determined route throughout the neighborhood that includes walking up one side of the street and back down the other side of the street before moving on to an adjacent block, and the next adjacent block, etc. The block order will be pre-determined by the data analyst performing randomization to where blocks will be ordered as closet to concentrically in a clockwise manner from the first block.

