If more than one household resident is interested and eligible in the study, the person with the most recent birthday will be enrolled. One participant per household is eligible. The CC team will conduct an informed consent with all participants. The CC team will then administer a demographic and baseline survey and directly enter data into REDCap. If the resident is interested in the study but is not available or able to complete the baseline survey at the time of the first encounter, CC team will conduct the Informed Consent Process (resident will sign the Informed Consent Form) and then identify a time to reschedule complete the baseline survey. If necessary, the CC team can schedule to meet with the resident virtually to complete the baseline survey.

Completion of the baseline survey indicates resident is fully enrolled in the study and is to be considered the official date of enrollment.

If there are one or more children ages 3-17 living in the household, the child or children's primary caregiver will be given the option of completing an additional follow-up survey regarding their child's health and wellbeing. One participant per household is eligible to complete the children's health and well-being survey for up to three children residing in the household. If more than three children ages 3-17 reside in the household, the enrolled caregiver will be asked to complete the survey for the three children with the most recent birthdays. We will enroll adult caregivers of approximately 480 children ages 3-17. To meet this goal, approximately up to 240 additional caregivers will be enrolled. Towards this end, after enrollment of adult subjects is complete within a microcluster, CC teams will continue to enroll caregivers from homes within a microcluster with which contact has not already been made. Enrollment will end when either enough caregivers are enrolled for up to 10 children per microcluster or two weeks after adult enrollment closes within the microcluster.

Subject compensation

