Several Community Coordinator (CC) teams will be recruiting participants. A given team of two will remain in a microcluster until at least 8participants are fully enrolled in that microcluster. They will then move to the next microcluster on the randomly generated list. Multiple microclusters will be undergoing enrollment simultaneously. The CC team will be blinded to what arm of the trial the microcluster is in until all participants are enrolled. Participants will also be blinded until after everyone in that cluster is enrolled.

When starting recruitment in a new microcluster, the CC team will first place door knockers on all homes within the microcluster boundaries to alert neighbors to the presence of the study team in the neighborhood. They will then begin door-to-door recruitment at a pre-determined house that is closest to the geographic center of the study microcluster. They will follow a pre-determined route throughout the neighborhood that includes walking up one side of the street and back down the other side of the street before moving on to an adjacent block, and the next adjacent block, etc. The block order will be pre-determined by the data analyst performing randomization to where blocks will be ordered as closet to concentrically in a clockwise manner from the first block.

For a given house, a potential participant will be screened by the CC team to determine eligibility:

Key Inclusion Criteria:

- At least 18 years of age
- Have the ability to communicate via text messaging

- Individuals comfortable communicating in English
- A permanent resident of the home where they are to be enrolled
- Have knowledge of their household finances

Key Exclusion Criteria:

- Individuals who plan to move out of the study microcluster within 6 months
- Individuals who are unable to fully consent and participate based on CC team assessment

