If more than one household resident is interested and eligible in the study, the person with the most recent birthday will be enrolled. One participant per household is eligible. The CC team will conduct an informed consent with all participants. The CC team will then administer a demographic and baseline survey and directly enter data into REDCap. Participants will be compensated \$40 after the baseline survey using ClinCards, \$15 after a 6 month check in, \$15 after a 12 month check in, \$15 after an 18 month check in, and \$40 after a follow up survey. Follow up data collection will occur between September 2024 and March 2025, with each participant surveyed roughly 24 months after their initial enrollment date.

For all households including one or more children ages 3-17 living in the household, the child or children's primary caregiver will be asked to complete an additional follow-up survey regarding their child's health and well-being, for up to three children per household. If more than three children ages 3-17 reside in the household, the enrolled caregiver will be asked to complete the survey for the three children with the most recent birthdays. Participants who complete the follow-up survey regarding children's health will be compensated \$20 after survey completion.

To support recruitment efforts, we will partner with community organizations to widen the reach of study promotion and to improve dissemination of recruitment materials, particularly in communities where recruitment is found to be difficult. We will also use a community-facing website to promote the study and increase screening for enrollment.

Respondent Driven Sampling

IGNITE referrals. Respondent driven sampling will be implemented to drive enrollment when Community Coordinators identify that completing enrollment (i.e., reaching at least 8 participants) is difficult in a particular microcluster. This strategy will be implemented only as a contingency.

Participants will then be invited to refer individuals who they think may be willing to participate in the study. If those referrals meet eligibility criteria and are successfully enrolled, the participant who made the initial referral will receive a payment of \$10 via their ClinCard for that successful referral.

Participants can make an unlimited number of referrals, but only up to 2 referrals will be enrolled per participant (to limit referral networks at a max of four networks per cluster.)

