The rationale for providing these services as part of this study follows from a large literature linking economic and financial security to health and well-being.^{4–6} While these services are generally available to all Philadelphians, informational and time constraints (current models of delivery require individuals to reach out to ask for services) and budgetary constraints on the partner side remain barriers to engagement. The goal of the financial intervention in this study is to increase access to these services by increasing financial capacity among the partner organizations and reducing barriers among potential beneficiaries.

The intervention group will be provided the above package of financial services using the following general approach. Within one month of enrollment and completing the baseline survey, the research team will contact intervention group participants, provide information on each of the financial partners, as well as a checklist for

financial documents needed to have on hand to work with each partner. At that time, intervention group participants will select a pre-filled appointment slot with the Clarifi team for their initial intake. This appointment can either be in-person or virtual, depending on the participant's preference. Intervention group participants will receive text-message reminders in advance of their initial appointment, as well as a follow up text to assess whether they attended the appointment after the intended date and time. In the event participants were unable to participate, the research team will reschedule the initial session and again confirm participation via text-message. Participants will be eligible to receive their one-time \$400 at this initial session, which will be delivered in the form of a check or direct deposit based on participant preference. After this initial meeting, the research team will help participants schedule a second appointment (and any subsequent appointments, as needed), following the same strategy.

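### First financial contact is due within a month of each person's own enrolment, but arm must stay hidden until the whole microcluster is enrolled; in intervention clusters open longer than a month both rules cannot be met.

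*Combined protocol and SAP*

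**What the plan says.** Four elements matter.

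- **Contact rule** (Section 8.2, Individual and Household-Level Financial Interventions): "Within one month of enrollment and completing the baseline survey, the research team will contact intervention group participants". At that contact they receive information on the partner organizations and choose an appointment for the initial session, where the $400 grant becomes available.
- **Date of enrolment** (Section 6): "Completion of the baseline survey indicates resident is fully enrolled in the study and is to be considered the official date of enrollment". The month is therefore counted from a personal date.
- **Blinding rule** (Section 6, repeated in Section 8.2, Enrollment): "The CC team will be blinded to what arm of the trial the microcluster is in until all participants are enrolled", and "Participants will also be blinded until after everyone in that cluster is enrolled". This rule is counted from a cluster date.
- **Length of cluster enrolment**: set by a head count and not by time. Section 6 has "A given team of two will remain in a microcluster until a total of 12 participants are fully enrolled in that microcluster", while Section 8.2 has "A given team of two will remain in a microcluster until at least 8participants are fully enrolled in that microcluster".

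Two further provisions lengthen enrolment. In clusters that are hard to fill, "Respondent driven sampling will be implemented to drive enrollment when Community Coordinators identify that completing enrollment" is difficult, with $10 paid per successful referral. Section 6 adds that "after enrollment of adult subjects is complete within a microcluster, CC teams will continue to enroll caregivers", for up to two weeks.

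The order enrol everyone, reveal the arm, then act is written out for tree planting only (Section 8.2, Tree planting).

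**The concern.** Clusters are randomized before anyone is approached, so blinding during recruitment is the trial's own protection against enrolling different kinds of people in the two arms. Contact about the financial partners and the grant tells a participant which arm the cluster is in. If that happens while the team is still recruiting, people drawn by cash or benefits help may join intervention clusters more readily, with no counterpart in control clusters.

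The slow clusters are also where referral recruitment is planned, so a participant who already knows about the grant could be inviting neighbours. The constrained randomization balanced area-level census and land measures, not who agrees to take part. Both primary outcomes are self-reported.

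**Working it through.** The plan gives no figure on this point to reproduce. The check is whether the two rules can coexist, and then how often they might collide.

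**Step 1: compatibility.** Let D be the time from first to last enrolment in an intervention cluster. Contact with the first enrollee is due by 1 month; the blind lifts at D. Both rules can be met only if D ≤ 1 month. Nothing in the documents limits D. Because the contact rule is a deadline with no earliest date, read alone it would also permit contact in a faster cluster that is still recruiting.

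**Step 2: people exposed in a slow cluster.** Assume m people enrol at an even pace, person i at time (i − 1) × D/(m − 1), and count those enrolled after month 1.

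| D (months) | m = 8 | m = 12 |
|---|---|---|
| 1.5 | 3 | 4 |
| 2 | 4 | 6 |
| 3 | 5 | 8 |

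Example: with m = 8 and D = 2, the last four enrol at 1.14, 1.43, 1.71 and 2.00 months.

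**Step 3: average time a cluster is open.** If each team works through clusters one after another, mean open time μ = window × teams / 60. The documents say only that there are several teams, so 2 to 10 is an assumption. The window is itself inconsistent:

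- 9 months in Section 5.2.
- About 19 months in Section 6 (September 2022 to March 2024).
- About 7 months implied by surveying everyone at 24 months between September 2024 and March 2025.
- The dates in Section 8.2, Enrollment, end before they begin.

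Results: 9 × 4/60 = 0.60; 9 × 6/60 = 0.90; 9 × 7/60 = 1.05; 19 × 3/60 = 0.95; 19 × 4/60 = 1.27 months. The mean first exceeds one month at 7 teams (9-month window) or 4 teams (19-month window).

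**Step 4: share of clusters with D over one month.** Assume Poisson enrolment at rate m/μ per month, equal across clusters. Then D > 1 if at most m − 2 people enrol in the month after the first, so P(D > 1) = P(Poisson(m/μ) ≤ m − 2). For m = 8:

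| Window, teams | μ (months) | P(D > 1) | Of 30 intervention clusters |
|---|---|---|---|
| 7 months, 4 | 0.47 | 0.2% | 0.1 |
| 7 months, 6 | 0.70 | 6% | 1.9 |
| 9 months, 4 | 0.60 | 2% | 0.6 |
| 9 months, 6 | 0.90 | 22% | 6.5 |
| 19 months, 3 | 0.95 | 26% | 7.9 |
| 19 months, 4 | 1.27 | 56% | about 17 |

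With m = 12 the picture is similar: 1% at μ = 0.60, 28% at 0.95 and 65% at 1.27. Unequal recruitment rates would lengthen D in the hard clusters beyond these figures.

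**The case against.** The strongest reply is that the blinding rule is explicit and stated twice, the tree-planting text follows it, and the financial text describes itself as a general approach. On that reading the blind holds and early enrollees are simply contacted late. The definition of the intervention period for the administrative-data analysis, which starts when enrolment and baseline collection end, points the same way. This reading is available, and it defeats the inference that slow clusters will in fact be unblinded: the documents do not say that. It does not settle the conflict. The administrative-data definition is written for another purpose. Section 5.2 also starts the interventions in quarter 3 of Year 2, while nine months of baseline collection beginning in Year 2 cannot finish before that quarter ends.

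A reader might also infer that overruns would be common. That is not supported. It needs the 19-month window, which other sections contradict, or a large number of teams.

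A third tempting reading is that caregiver enrolment falls outside the blind, exposing up to 240 more people. Section 5.4 counts these caregivers as additional participants, so a rule covering all participants can already include them. The 240 are also spread over both arms, and only intervention clusters are contacted. What remains is an ambiguity worth one clause.

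Safeguards do limit the harm. Recruitment follows a fixed door-to-door route with most-recent-birthday selection, referral sampling is a contingency with at most two enrolled referrals per participant, and the models adjust for the baseline outcome and observed individual imbalances. These reduce selection; they do not remove selection on unmeasured motivation. Assigning the contact to staff other than the coordinators would not help, since participants must stay blinded too.

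**Conclusion.** The point stands as an unreconciled conflict between two timing rules. It affects only intervention clusters whose enrolment spans more than one month; there the rules are incompatible and the protocol gives neither precedence. If the contact rule prevails, arm is disclosed during open recruitment: with 8 people enrolled evenly over two months, half of them join after the first contact falls due.

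The number of clusters affected cannot be determined from the documents. It ranges from almost none to more than half under assumed team numbers, the competing recruitment windows and Poisson enrolment. The size of any resulting bias cannot be estimated either. The matter is still worth correcting before recruitment, because it touches the trial's main protection against selective enrolment and the correction is nearly free.

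**What to change.** Reconcile Section 6 with the Enrollment, Respondent Driven Sampling and financial-intervention text of Section 8.2:

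1. Tie the first financial contact to the cluster reveal, as the tree-planting text does; for example, within one month of closure of the microcluster's enrolment, replacing the count from each person's enrolment.
2. Define closure as the end of adult, referral and caregiver enrolment, so that the blinding rule's reference to all participants is unambiguous.
3. State that the arm is disclosed to coordinators and participants only after closure, and that this takes precedence over any contact deadline.

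Recording each cluster's first and last enrolment dates and its reveal date would let adherence be reported.

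The cost is a wording change. The one downside is that early enrollees in slow clusters are first contacted some weeks later, and so have a somewhat shorter time with the financial services before the intervention period ends in August 2024.

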For this cluster randomized trial, we assume a Type I error rate of 0.05 and a desired power of 0.8 for the primary outcomes. Our study will include 60 microclusters (30 intervention, 30 control) with at least 8 participants in each cluster (n=480 across all clusters). We will have no fewer than 480 and can enroll up to 720. The number of participants enrolled will depend on our dynamic enrollment strategy that we've discussed already. We assume an intraclass correlation (ICC) of 0.05. For our primary outcomes (and all survey-based outcomes), we will fit a marginal model using generalized estimating equations (GEE) to estimate the effect of the intervention relative to control. Under these assumptions, we will be able to detect an intervention effect of 0.33 s.d at 80% power with 30microclusters per arm (60 total) and 8 participants per microcluster.⁹ This is a conservative estimate of power since we will adjust for the baseline value of the outcome and other covariates associated with the outcome. If we are only able to sample from 50 microclusters (25 per arm; n=400 across all clusters), we will be able to detect a moderate effect size of 0.37 s.d. at 80% power. Assuming up to 25% attrition between baseline and endline, we would still be able to detect a treatment effect of 0.31 s.d.

Statistical Analysis

Individual-level primary and secondary outcomes

For all primary and secondary outcomes drawn from our two-wave survey of 720 trial participants, we will assess differences in outcomes between the intervention and comparison groups using Generalized Estimating Equation models (GEE) that account for clustering at the study microcluster level. We will use canonical link functions for all outcomes. All models will adjust for the baseline level of the outcome, all microcluster-level characteristics used in the covariate constrained randomization (see randomization protocol),¹⁰ any individual characteristics found to be imbalanced between the intervention and control groups at baseline.

We will conduct an intention-to-treat analysis: participants that move out of (or across) study clusters, separately engage with community partner services while in the control group, or do not engage with these services while in the treatment group will all be considered exposed to their original treatment assignment.

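### The 0.31 SD quoted as detectable after 25% attrition names no base and, unadjusted, is not supported at the 480 minimum, where the stated inputs give 0.34 SD

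*Combined protocol and SAP*

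**What the plan says.** Everything quoted here is in Section 9. Under Power Calculations the plan sets its error rates: "we assume a Type I error rate of 0.05 and a desired power of 0.8 for the primary outcomes". It assumes an ICC of 0.05 and 60 microclusters with at least 8 participants each, 480 in all. On enrolment it says "We will have no fewer than 480 and can enroll up to 720".

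Three detectable effects follow:

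- For 480 enrolled: "we will be able to detect an intervention effect of 0.33 s.d at 80% power with 30microclusters per arm (60 total"), with 8 participants per microcluster.
- For a fallback to 50 clusters and 400 participants: "we will be able to detect a moderate effect size of 0.37 s.d. at 80% power".
- After loss to follow-up: "Assuming up to 25% attrition between baseline and endline, we would still be able to detect a treatment effect of 0.31 s.d".

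After the first figure the plan comments: "This is a conservative estimate of power since we will adjust for the baseline value of the outcome". Under Statistical Analysis it commits to that adjustment: "All models will adjust for the baseline level of the outcome". Neither place gives an R-squared or a correlation between baseline and endline.

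**The concern.** The third figure runs the wrong way. Losing a quarter of the participants cannot make a trial sensitive to a smaller effect if the clusters, alpha, ICC and adjustment stay the same. Yet 0.31 lies below both figures given without attrition. Something must therefore have changed between the sentences, such as the enrolled total, the alpha or an allowance for covariates, and the text does not say what.

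This is the plan's only power figure that allows for attrition, and the primary endpoint is measured 24 months after enrolment. Enrolment may end anywhere from 480 to 720, with a 50-cluster fallback. A reader who later has to interpret a null result needs to know which sample gives which sensitivity, and one unlabelled number cannot show that.

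**Working it through.** **Inputs.** From Power Calculations: alpha 0.05, power 0.80, ICC 0.05, 30 clusters per arm (25 in the fallback), 8 enrolled per cluster at the minimum, attrition 25%. An enrolment of 720 over 60 clusters is 12 per cluster. My assumptions: a two-sided test (sidedness is not stated), equal cluster sizes, attrition spread evenly over clusters, and no covariate adjustment except where R² appears.

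**Formulas.** With k clusters per arm, m analysed per cluster and K = 2k:

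- SE = sqrt{ (1 − R²) × 2 × [1 + (m − 1) × ICC] / (k × m) }, in SD units, with R² taken as equal at cluster and individual level
- Detectable effect = (t at 0.975 + t at 0.80, on K − 2 df) × SE. The z version uses normal quantiles.

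**Step 1: the plan's figures without attrition.**

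- 60 × 8: the design effect is 1 + 7 × 0.05 = 1.35. SE = sqrt(2 × 1.35 / 240) = 0.1061. On 58 df the multiplier is 2.850, giving 0.302 (z: 2.802, giving 0.297). The plan says 0.33.
- 50 × 8: SE = sqrt(2 × 1.35 / 200) = 0.1162. On 48 df the multiplier is 2.860, giving 0.332 (z: 0.326). The plan says 0.37.

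Neither figure is reproduced. Both appear if alpha is 0.025 with t (0.334 and 0.368), or at alpha 0.05 if the ICC is about 0.09 (t) or 0.10 (z). None of these inputs is stated.

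**Step 2: the figure after attrition.** At 480 enrolled, 8 × 0.75 = 6 analysed per cluster. The design effect is 1.25 and SE = sqrt(2 × 1.25 / 180) = 0.1179. The detectable effect is 0.336 by t and 0.330 by z, not 0.31.

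**Step 3: direction.** Going from 8 to 6 per cluster multiplies the detectable effect by sqrt[(1.25/6) / (1.35/8)] = 1.111. On a 60 × 8 base, 0.31 after attrition would need 0.31 / 1.111 = 0.279 before it. That is below both the plan's 0.33 and the 0.30 its inputs give.

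**Step 4: all three enrolment scenarios**, at ICC 0.05 and two-sided alpha 0.05, unadjusted, t (z in brackets):

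| Enrolled | Before attrition | After 25% attrition | Power for 0.31 after attrition |
|---|---|---|---|
| 480 (60 × 8, then 6) | 0.302 (0.297) | 0.336 (0.330) | 73.5% (74.9%) |
| 400 (50 × 8, then 6) | 0.332 (0.326) | 0.369 (0.362) | 65.3% (67.0%) |
| 720 (60 × 12, then 9) | 0.264 (0.260) | 0.290 (0.285) | 84.9% (86.1%) |

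**Step 5: covariate gain needed for 0.31 after attrition.** The required R² is 1 − (0.31 / unadjusted effect)².

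- 480 enrolled: 1 − (0.31/0.3358)² = 0.148 by t; 1 − (0.31/0.3302)² = 0.118 by z
- 400 enrolled: 0.295 by t; 0.265 by z
- 720 enrolled: none

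**The case against.** The strongest reply is that the sentence never ties 0.31 to 480, and that the documents offer two routes to it. Section 6 has teams stay until 12 are enrolled per microcluster, and Statistical Analysis speaks of 720 trial participants. At 720 the effect after attrition is about 0.29, so 0.31 would be true. Alternatively, every model adjusts for the baseline outcome, and 12% to 15% explained variance at 480 is a modest requirement: a baseline correlation of about 0.34 to 0.38 (the square roots of 0.118 and 0.148) if baseline were the only covariate. Both points stand, and for that reason the planned adjusted analysis is not shown to fall short. But 720 is a maximum, the Enrollment text in Section 8.2 lets teams move on after 8, and no correlation is given. The plan also uses the adjustment to call its 0.33 conservative, which implies that 0.33 is unadjusted; moving to an adjusted figure two sentences later would have to be declared.

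A second reply is that power may have been reckoned at alpha 0.025 because there are two primary outcomes. That gives 0.334, 0.368 and, at 720 with attrition, 0.321 by t; by z it gives 0.327, 0.358 and 0.314. The t version misses 0.31 and the z version misses 0.37, so no single convention yields all three. The stated rate is 0.05, and at 0.025 the 480 minimum after attrition rises to 0.36 to 0.37, which leaves 0.31 further off.

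A one-sided 0.05 test would give 0.293 to 0.297 at 60 × 6 and so reach 0.31. It would also give 0.26 to 0.27 at 60 × 8, further from the plan's 0.33.

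The 65% power figure combines the fallback, the full attrition allowance and no covariate gain, and the plan does not attach 0.31 to that case. It is a lower bound for orientation.

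**Conclusion.** The concern holds. The 0.31 SD has no stated base, and the plan's own inputs do not deliver it at the minimum of 480. Unadjusted, 480 enrolled with 25% attrition gives 0.34 SD by t (0.33 by z), and about 73% to 75% power for 0.31. This rests on a two-sided alpha of 0.05, ICC 0.05, equal cluster sizes and evenly spread attrition. It does not show that the adjusted analysis, or a trial that reaches 720, would miss 0.31.

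The 0.33 and 0.37 also fail to follow from the stated inputs, which give 0.30 and 0.33. Both are larger than necessary, so they err on the safe side. The three figures do not share one stated set of assumptions and cannot be checked as written. This should be corrected, but it does not threaten the design.

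**What to change.** Restate the Power Calculations paragraph with one declared alpha and its sidedness, saying whether it allows for the two primary outcomes. For each detectable effect give the number of clusters, the analysed size per cluster, the attrition and any assumed R-squared. At two-sided alpha 0.05 and ICC 0.05, unadjusted, the figures before and after 25% attrition are 0.30 and 0.34 SD for 480, 0.33 and 0.37 for 50 clusters (400), and 0.26 and 0.29 for 720. They must be recomputed if a different alpha is declared. Either remove 0.31 or state the base or R-squared that produces it. If 0.33 and 0.37 are kept, state the inputs behind them.

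The cost is protocol wording only: no extra participants, and no change to the estimand, test or analysis. At alpha 0.05 unadjusted, the post-attrition figure for the minimum sample becomes less favourable (0.34 instead of 0.31) and the two pre-attrition figures become more favourable (0.30 and 0.33 instead of 0.33 and 0.37). The choice of alpha should therefore be made explicitly.
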